### **6.5. Appendix 5: Statistical Methodology Details**

Statistical programming will be done using SAS version 9.4 (or later) on a Windows 10 Enterprise (or later) operating system. Plasma PK parameters will be calculated using Phoenix™ WinNonlin® (Version 8.3.4, Certara, LP).

#### **6.5.1. PK Analysis**

[figure not shown]
##### **6.5.1.1. Concentration**

#### **6.5.1.2. PK Parameters**

### **6.6. Appendix 6: Methods to Manage Missing Data**

#### **6.6.1. Rule for Missing Pre-dose Concentrations**

### **6.6.2. Missing Pre-dose Sampling Date/Times**

If a missing pre-dose concentration is also missing sampling date/time (due to the sample not being drawn), the sampling date/time will be imputed with the corresponding dosing date/time on that day.

### **6.6.3. BLQ Concentrations**

Concentration values that are reported as BLQ will be presented as “BLQ” in concentration listings, replaced by 0 for summary statistic calculations and linear-scale plots of concentrations, and excluded from semi-logarithmic-scale plots of concentrations.

For derivations of PK plasma parameters, all concentrations that are BLQ prior to the first measurable concentration will be set to zero. BLQ values that are between measurable concentrations will be set to missing. Measurable concentrations immediately between 2 BLQ values will be set to missing. Measurable concentrations following two or more consecutive BLQ concentrations will be set to missing. The BLQ values following the last quantifiable time points will be set to missing. No concentration estimates will be imputed for missing sample values.

### **6.6.4. Exposure**

#### **Missing Study Drug Dosing Information**

All efforts should be made to obtain missing study drug dosing information from the investigator. If data are still missing after all efforts, then total exposure will be missing.

#### **Missing Last Date of Study Drug Exposure**

All efforts should be made to obtain missing last date of study drug exposure from the investigator. If the last date of exposure is still missing after all efforts, then the last available dosing record date may be used as the last study drug exposure date for the calculation of exposure duration.

### **6.6.5. AEs**

#### **Missing AE Severity**

Missing AE severity must be queried until resolution. In the unlikely event that resolution is not possible, missing severity will be imputed as “severe” in summaries.

#### **Missing AE Relationship to Study Drug**

Missing relationship to study drug for a TEAE must be queried until resolution. In the unlikely event that resolution is not possible, missing relationship will be imputed as “related” in summaries.

#### **Missing AE Seriousness**

Missing AE seriousness must be queried until resolution. Seriousness cannot be imputed as “serious” since doing so would affect the reconciliation between the trial database and the SAE registry.

### **Missing AE Start Date/Time Information**

Note: partial times will not be recorded in the CRF.

An AE will be considered a run-in AE for the Run-In Safety Population under the following conditions:

- Missing start year, month, day, time and it can be deduced from non-missing components of AE end date that the AE ended before first IMP.
- Missing start month, day, time if start year is equal to or after year of first study drug during run-in and it can be deduced from non-missing components of AE end date that AE ended before first IMP.
- Missing start day and time if start year is after year of first study drug during run-in or if start year is equal to year of first study drug during run-in and month is equal to or after month of first study drug during run-in and it can be deduced from non-missing components of AE end date that AE ended before first IMP.
- Missing start time if start date is on or after date of first study drug during run-in and it can be deduced from non-missing components of AE end date that AE ended before first IMP.

An AE will be considered treatment emergent for the Safety Population under the following conditions:

- Missing start year, month, day, time unless it can be deduced from non-missing components of AE end date that the AE ended before first IMP.
- Missing start month, day, time if start year is equal to or after year of first IMP, unless it can be deduced from non-missing components of AE end date that AE ended before first IMP.
- Missing start day and time if start year is after year of first IMP or if start year is equal to year of first IMP and month is equal to or after month of first IMP, unless it can be deduced from non-missing components of AE end date that AE ended before first IMP.
- Missing start time if start date is on or after date of first IMP.

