10.1.1 Time Period for Collecting Adverse Events

Adverse event monitoring and reporting will begin after subjects sign the ICF, continue throughout the study and include EOS/ET/Follow-up. Subjects will be monitored by the study site staff for untoward effects and will be released from the study after the last procedure is completed and confirmed that the subject has no residual untoward effects from the study drug that may affect safety. Treatment-emergent AEs will be defined as events observed after starting administration of INDV-2000 or placebo. For Part III, run-in AEs will be defined as events observed after starting SUBOXONE SL film and before starting INDV-2000.

Surgical procedures, planned before enrolment of the subject in the study, are not considered AEs if the condition was known before study inclusion. In this case the medical condition is to be reported in the subject's medical history.

Any clinically significant symptoms will be reported as AEs. All AEs and corresponding treatment will be recorded in the eCRFs and a summary of all safety data will be presented in the final Clinical Study Report (CSR). Any ongoing AEs will be appropriately followed up until resolution or 14 days after EOS/ET. If findings are noted in the 90 day post last dosing day safety follow up call for male participants, these will be recorded as Adverse Events and followed until completion of required assessments. The study site personnel will make every effort to contact the subject as outlined in Section 6.6.2, after which the outcome of the AE will be considered ongoing and the subject will be noted in source as lost to follow-up.

If a subject experiences the onset of an SAE within 5 days following study completion and in the opinion of the Investigator, that SAE is associated with the study drug, it will be followed and reported as described in Section 11.2.

Confidential Page 56 of 108

If an SAE occurs that is deemed related to study drug, a PK sample will be taken as soon as possible after the event is reported. If possible, an additional sample should be collected when the SAE has been resolved.

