### **5.5.2. Adverse Events**

A TEAE is an AE that started at or after first administration of IMP. A run-in AE is an AE that started at or after first administration of study drug during the run-in period. AEs will be assigned to study treatments based on start dates and times of treatments and start dates and times of AEs.

AEs will be coded to a System Organ Class (SOC) and Preferred Term (PT) using Medical Dictionary for Regulatory Activities (MedDRA). Additional details of the coding process, including the current version of the dictionary, are described in the Data Management Plan. All AEs will be listed for individual subjects. Listings will include SOC, PT, and reported term; treatment; onset date and time, end date, and duration; run-in status, treatment-emergence, severity, toxicity grade (though not required for Part III of the study), seriousness and seriousness criteria; relationship to study drug; action taken with IMP; action taken with SUBOXONE SL film; whether concomitant treatment was given; outcome; and whether the AE resulted in study discontinuation. Duration (days) is calculated as the AE end date – the AE onset date +1; for ongoing AEs, the date of end of study participation will be used as the end date. Duration will be missing if either the start or end date is partially or completely missing. SAEs, TEAEs leading to IMP discontinuation or interruption, AEs leading to SUBOXONE SL film discontinuation or interruption, and fatal AEs will be listed separately.

The incidence and number of all TEAEs, TESAEs, study drug-related TEAEs and TESAEs, severe TEAEs, TEAEs leading to IMP discontinuation or interruption, and fatal TEAEs will be presented in an overall summary table.

TEAEs, TESAEs, study drug-related TEAEs and TESAEs, and run-in AEs will be summarized by MedDRA SOC and PT, each in descending order of frequency among all subjects within study part (then alphabetically in case of ties). TEAEs will also be

summarized by maximum severity within SOC and PT. If an AE is reported more than once by a subject within a SOC and/or PT, the maximum reported level of severity will be used at each level of summation in the severity summary table.

Incidence and number of TEAEs will also be summarized by PT only (ie, not SOC), sorted by descending frequency among all subjects (within study part).

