Non-treatment-emergent, non-run-in AEs are defined as AEs that started either before first administration of study drug or after the run-in period but before first administration of IMP and will be summarized for the run-in safety population.

See Section [6.6.3 \(Appendix 6\)](#) for details on handling of missing AE information.

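### The missing-start rules for run-in AEs test when the event ended, so some AEs with a known run-in start miss the run-in summary and some screening AEs are labelled run-in

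*SAP*

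**What the plan says.** SAP 5.5.2 sorts AEs by onset into three groups:

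- Treatment-emergent: "A TEAE is an AE that started at or after first administration of IMP".
- Run-in: "A run-in AE is an AE that started at or after first administration of study drug during the run-in period".
- Neither, summarised for the Run-In Safety Population: "AEs that started either before first administration of study drug or after the run-in period but before first administration of IMP".

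Protocol 10.1.1 also uses onset: "run-in AEs will be defined as events observed after starting SUBOXONE SL film and before starting INDV-2000".

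SAP 6.6.5, under Missing AE Start Date/Time Information, gives four run-in bullets, one for each degree of missingness:

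1. Whole start missing: "Missing start year, month, day, time and it can be deduced from non-missing components of AE end date that the AE ended before first IMP".
2. Year known: "Missing start month, day, time if start year is equal to or after year of first study drug during run-in", plus ended before first IMP.
3. Year and month known: the same pattern, with a start in the run-in year accepted if "month is equal to or after month of first study drug during run-in", plus ended before first IMP.
4. Only the clock time missing: "Missing start time if start date is on or after date of first study drug during run-in", plus ended before first IMP.

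The first three TEAE bullets in the same section carry an exclusion for AEs that can be shown to have ended before first IMP. The fourth TEAE bullet looks only at whether the start date reaches the date of first IMP.

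**The concern.** The end-before-IMP test appears in neither definition of a run-in AE, and it has two effects.

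(a) It rejects AEs that began in run-in and persisted into INDV-2000 dosing. With only the clock time missing, the date already shows that the AE began before IMP, so the TEAE rule rejects it as well. The residual group does not cover it either.

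(b) The bullets never use the end date at the other boundary. Nothing excludes an AE that had demonstrably ended before any SUBOXONE was given.

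Part III describes safety under SUBOXONE alone, then both drugs, then INDV-2000 alone. The run-in AE table is part of the SUBOXONE-only background. Fault (a) is selective, because it removes only AEs that lasted into INDV-2000 dosing. Fault (b) adds events that no study drug preceded.

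**Working it through.** The plan states no figure on this point, so the check applies the bullets literally.

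**Timeline.** First SUBOXONE is on Day -6 and first INDV-2000 on Day 3 (SAP 1.2; protocol 22.3). There is no Day 0, so the gap is 8 calendar days. For illustration, put Day -6 on 25 January; Day 3 is then 2 February.

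| Start as recorded | End | Run-in bullet | TEAE bullet | SAP 5.5.2 residual group | Result |
|---|---|---|---|---|---|
| 27 Jan (Day -4), time missing | 4 Feb | No: not ended before IMP | No: date before IMP | No | No group |
| 25 Jan (Day -6), time missing | Ongoing | No | No | Cannot be decided without the time | No group by the rules |
| January, day missing (true start 27 Jan) | 5 Feb | No | No: month before IMP month | No | No group |
| Wholly missing, year only, or January only | 10 Jan | Yes | No | Not applied | Run-in, though ended 25 - 10 = 15 days before SUBOXONE |
| 5 Jan, time missing | 10 Jan | No: date before run-in | No | Yes | Correct |
| 31 Jan (Day 1), time missing | 1 Feb | Yes | No | Yes | Two labels |

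**How often each pattern meets the fault.** Place first SUBOXONE on each of 366 consecutive dates. Take every true start from 28 days before SUBOXONE up to Day 2, with complete end dates or ongoing. The results are shares of patterns, not event rates.

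*Fault (a): true start Day -6 to Day -1, lasting past first IMP.* The start precedes IMP by 8, 7, 6, 5, 4 or 3 days, a mean of 33/6 = 5.5. The AE is left with no group when a boundary of the known unit falls in that gap.

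- Time missing: always, 100%.
- Day missing: 12 month ends, 5.5 × 12/366 = 18.0%.
- Month missing: 1 year end, 5.5 × 1/366 = 1.5%.
- Whole start missing: 0%; all go to TEAE.

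*Fault (b): screening AE that ended before first SUBOXONE.* A start k days before SUBOXONE has k possible end dates, so the weighted mean lead is Σk²/Σk for k = 1 to 28, which is 7714/406 = 19 days. The AE escapes the run-in label only if a boundary falls in that lead.

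- Whole start missing: labelled run-in in 100%.
- Month missing: 1 - 19/366 = 94.8%.
- Day missing: 1 - 19 × 12/366 = 37.7%.
- Time missing: 0%, because bullet 4 bounds the start by date.

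Fault (a) therefore sits mainly in bullet 4, and fault (b) in bullets 1 to 3.

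**The case against.** The strongest reply is that SAP 5.5.2 governs. The bullets say when an AE will be considered run-in; they do not say only then. A Day -4 onset satisfies the definition without a clock time, so nothing needs imputing. This is a fair reading, and if adopted it would rescue most of fault (a). But the SAP does not state that order of precedence, and bullet 4 is written for exactly this case. The reading does not settle an onset on the Day -6 date with the time missing, or a start known only to a month that spans screening and run-in. It does not touch fault (b).

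The second reply is that the situation is rare, and it largely stands. Subjects are in the clinic from Day -6, with AE assessment on every run-in day, so incomplete onsets should be few. Fault (b) needs an AE recorded before Day -6. Protocol 10.1.1 collects AEs from consent, but the Part III schedule in protocol 22.3.1 marks AE assessment only from Day -6.

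A reader might also infer more than the documents support:

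- That the rules set no lower bound at all. Bullets 2 to 4 bound the start by year, by year and month, or by date. Only bullet 1 has no bound.
- That the events vanish from the report. SAP 5.5.2 lists all AEs, with run-in status and treatment emergence.
- That the primary analysis is distorted. Neither fault moves an event into or out of the TEAE tables.
- That each affected subject shifts a rate by 1/16 = 6.25%. Run-in AEs are summarised for the Run-In Safety Population, which includes run-in failures and whose size the documents do not give.

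**Conclusion.** The point holds as a minor defect of the SAP. Read literally, the missing-start bullets contradict the onset-based definitions. They leave AEs that began in run-in and lasted past first IMP out of the run-in summary: always when only the time is missing, sometimes when the day or month is missing. They also label as run-in some AEs that had ended in screening. The effect is confined to the run-in AE table and, through it, the residual group. Primary TEAE counts stand.

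The pattern shares (100%, 18.0% and 1.5% for the gap; 100%, 94.8% and 37.7% for the screening error) assume complete end dates and equal weight for every pattern. They show which bullets fail, not how many events will be affected. That number is unknown and probably low.

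A related inconsistency belongs with this one. Day 1-2 onsets are run-in under protocol 10.1.1 and non-run-in under SAP 5.5.2. Bullet 4 labels them run-in if they ended before IMP.

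**What to change.** Three changes to SAP 6.6.5:

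1. Drop the end-before-IMP test where the known start components already fall before first IMP. Keep it only where the start could lie on either side.
2. Add to run-in bullets 1 to 4 an exclusion for AEs whose known end-date components show that they ended before first study drug in run-in, parallel to the exclusion in the TEAE bullets.
3. Reconcile the status of Day 1-2 onsets between protocol 10.1.1 and SAP 5.5.2, and use the same upper bound in the bullets.

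In the same enumeration, changes 1 and 2 bring both faults to 0% for every degree of missingness. That test left Day 1-2 onsets as run-in, so change 3 must be decided separately. One side effect should be accepted openly. Among screening AEs that last past IMP, 24.1% of patterns with day missing and 2.2% with month missing become run-in, because the recorded start cannot separate screening from run-in.

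The cost is SAP wording and a few lines of code. No new data are needed.

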### **6.6.6. Medications and Therapies**

#### **Missing End Date/Time Information**

Note: partial times will not be recorded in the CRF.

Run-in and concomitant status will be assigned as follows:

A medication/therapy will be considered run-in under the following conditions:

- Missing end year, month, day, time and it can be deduced from non-missing components of the start date that the medication/therapy started before or during run-in.
- Missing end month, day, time if end year is equal to or after start year of run-in and it can be deduced from non-missing components of the start date that the medication/therapy started before or during run-in.
- Missing end day and time if end year/month is equal to or after start year/month of run-in and it can be deduced from non-missing components of the start date that the medication/therapy started before or during run-in.
- Missing end time if end date is on or after start date of run-in and it can be deduced from non-missing components of the start time that the medication/therapy started before or during run-in.

A medication/therapy will be considered concomitant under the following conditions:

- Missing end year, month, day, time and it can be deduced from non-missing components of the start date that the medication/therapy started before or during post run-in.
- Missing end month, day, time if end year is equal to or after start year of post run-in and it can be deduced from non-missing components of the start date that the medication/therapy started before or during post run-in.
- Missing end day and time if end year/month is equal to or after start year/month of post run-in and it can be deduced from non-missing components of the start date that the medication/therapy started before or during post run-in.
- Missing end time if end date is on or after start date of post run-in and it can be deduced from non-missing components of the start time that the medication/therapy started before or during post run-in.

## **6.7. Appendix 7: Data Set Descriptions**

Trial data sets will consist of CRF exports and external data files. External files may be used for protocol deviations and data from the central laboratory, for example.

